Subject completion for subjects in the treatment holiday group is defined as completion of the 24-week treatment holiday period plus the belimumab re-introduction treatment period to Week 52. Subject completion for subjects in the control and long-term discontinuation groups is defined as completion of all visits to Week 52.

Protocol waivers or exemptions are not allowed with the exception of immediate safety concerns. Therefore, adherence to the study design requirements, including those specified in the Time and Events Table, are essential and required for study conduct.

Supplementary study conduct information not mandated to be present in this protocol is provided in the accompanying Study Procedures Manual (SPM). The SPM will provide the site personnel with administrative and detailed technical information that does not impact subject safety.

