6. STUDY POPULATION ANALYSES

6.1. Overview of Planned Demography, Baseline Characteristics and Medical History Analyses

The study population analyses including analyses of subject's disposition, protocol deviations, demographic and baseline characteristics, medical conditions, prior and concomitant medications, and exposure and treatment compliance will be based on the ITT population, or for the Screened population where specified. Data will be presented by treatment group and for all subjects combined, unless otherwise specified.

Full details of data displays being presented in Appendix 11: List of Data Displays.

Completion and withdrawal status by treatment phase is defined in Section 13.6.2.

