13.3. Appendix 3: Assessment Windows

13.3.1. Mapping of the Maintenance Phase Visits for Subjects with an Escape Visit

In the eCRF, the next visit provided following the Escape visit is the Year 2 Week 8 visit, when chronologically the next visit would be the Year 2 Week 4 visit. Therefore, the maintenance phase visits for subjects with an Escape visit will be re-mapped in the ADaM analysis data sets to the maintenance phase visit, so that the visits align chronologically with those for subjects who complete the 52-week treatment phase and subsequently enter the maintenance phase.

	SDTM Variable	ADAM Variable							
Domain	VISITNUM VISIT	AVISITN AVISIT							
All	190 ESCAPE	190 ESCAPE							
All	220 YEAR 2 WEEK 8	210 YEAR 2 WEEK 4							
All	230 YEAR 2 WEEK 12	220 YEAR 2 WEEK 8							
All	240 YEAR 2 WEEK 16	230 YEAR 2 WEEK 12							
The mapping wi	The mapping will continue in this pattern for subsequent visits.								

If an Escape visit is present, mapping will occur as follows:

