13.6.2. Study Population

Demographics

Study Phases Definitions for Disposition

- Completion/withdrawal for the 52-Week Treatment Phase will be derived as follows:
 - Withdrawn if the subject completion status is marked as No and the subject has no visits during the maintenance phase.
 - Complete if the subject completion status is marked as Yes and the subject has no visits during the maintenance phase.
- Completion/withdrawal for the Maintenance Phase will be derived as follows:
 - Withdrawn if the subject completion status is marked as No and the subject has at least one visit during the maintenance phase.
 - Complete if the subject completion status is marked as Yes and the subject has at least one visit during the maintenance phase.

Age

- GSK standard IDSL algorithms will be used for calculating age where birth date will be imputed as follows:
 - Any subject with a missing day will have this imputed as day '15'.
 - Any subject with a missing date and month will have this imputed as '30th June'.
- Birth date will be presented in listings as 'YYYY'.
- Analysis age is derived in years relative to the Day 0 visit date, and is calculated in SAS as follows:

Analysis Age (years) INTCK('year', Date of Birth, Day 0 Date)

- (MONTH(Day 0 Date) < MONTH(Date of Birth)

Demographics

or (MONTH(Day 0 Date) eq MONTH(Date of Birth)

and $DAY(Day \ 0 \ Date) < DAY(Date \ of \ Birth)$)

Proteinuria

- For analysis, urine protein in g/24-hour will be approximated by the urine protein:creatinine ratio (uPCR).
- The value for reporting and analysis is stored in the uPCR result variable corresponding to the
 original unit in the SI dataset. Depending on the study, units for uPCR may be reported in g/g or
 mg/mg. As long as the units are the same in the numerator and denominator, the ratio will be
 the same.
- The SI dataset standard unit is reported in mg/mmol is not used for reporting and analysis purposes in this study.

Concomitant medications

- Concomitant medications are defined as
 - a. Medications that start on or before the Day 0 visit date and end on or after the Day 0 visit date, or
 - b. Medications that start after the Day 0 visit date
- Medications that meet criterion 'a' are considered to be in use at baseline.
- Medications will be assigned to the 52-week treatment or maintenance phases, as per the definitions in Section 13.4.1.
- Medications with partial or missing start and/or stop dates will be assumed to be concomitant

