13.7. Appendix 7: Reporting Standards for Missing Data

13.7.1. Premature Withdrawals

Element	Reporting Detail
General	Subject study completion (i.e. as specified in the protocol) was defined as s
	• Treatment holiday group: completion of the 24-week treatment holiday period plus the belimumab re-introduction treatment period to Week 52.
	• Control and long-term discontinuation groups: completion of all visits to Week 52.
	For reporting purposes, withdrawal from the maintenance phase is defined in Section 13.6.2.
	Withdrawn subjects were not replaced in the study
	All available data from participants who were withdrawn from the study will be listed and all available planned data will be included in summary tables and figures, unless otherwise specified.
	Withdrawal visits will be slotted as per Appendix 3: Assessment Windows or will be summarised as withdrawal visits.

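### The SAP's 52-week disposition rule gives no 52-week status to anyone with a maintenance-phase visit, so Table 1.5 would undercount completers in the holiday and control groups

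*SAP*

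**What the plan says.** SAP Section 13.6.2 derives disposition for two phases with four rules. For the 52-week phase they are "Withdrawn if the subject completion status is marked as No and the subject has no visits during the maintenance phase" and "Complete if the subject completion status is marked as Yes and the subject has no visits during the maintenance phase". The two maintenance-phase rules mirror these for subjects who do have a maintenance visit, for example "Complete if the subject completion status is marked as Yes and the subject has at least one visit during the maintenance phase". No third 52-week category, such as continued or escaped, is defined.

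SAP Section 6.1 makes this the governing derivation: "Completion and withdrawal status by treatment phase is defined in Section 13.6.2".

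Elsewhere the study defines completion without reference to maintenance. Protocol Section 3.1 states: "Subject completion for subjects in the control and long-term discontinuation groups is defined as completion of all visits to Week 52". SAP Section 13.7.1 repeats this as "Control and long-term discontinuation groups: completion of all visits to Week 52" and, for the holiday group, "Treatment holiday group: completion of the 24-week treatment holiday period plus the belimumab re-introduction treatment period to Week 52". Section 13.7.1 refers the reader to Section 13.6.2 only for withdrawal from the maintenance phase.

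The SAP expects subjects who have both a Week 52 visit and maintenance visits. Section 13.3.1 speaks of "subjects who complete the 52-week treatment phase and subsequently enter the maintenance phase" and re-maps visits for those who escape.

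**The concern.** A control subject who attends every visit to Week 52 and then takes up the maintenance option has completed the study as the protocol defines it, but is not complete for the 52-week phase under Section 13.6.2. A TH subject who re-starts belimumab before Week 24 has by definition not completed the holiday, yet with one later maintenance visit is not recorded as a 52-week non-completer either.

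The effect differs by group. SAP Section 13.4.1 restricts maintenance to TC and TH, so LTD is always classified while some TC and TH subjects may drop out of the 52-week count. Read across the columns of Table 1.5, completion in the two groups that receive belimumab could look lower than in LTD purely because of the derivation.

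**Working it through.** No sample size, power or error rate is involved and the plan states no figure to reproduce. The check applies the four rules to each possible subject path, then bounds the number affected.

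**Inputs**
- The four rules: SAP Section 13.6.2.
- Study definition of completion: Protocol Section 3.1 and SAP Section 13.7.1.
- Groups that can enter maintenance: TC and TH only (SAP Section 13.4.1).
- Escape route: TH subjects who re-start before Week 24 move to maintenance (Protocol Sections 3.1 and 4.4).
- Enrolled: 12 TH, 29 TC, 39 LTD, 80 in total (SAP Section 2.3).
- Cut-point rule: apart from Day 0, an assessment on a phase cut-point date belongs to the preceding phase (SAP Section 13.4.1). The Week 52, Exit and Escape visits are such cut-points (Section 13.4.1.1).

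**Step 1. Apply the rules**

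| Subject path | Recorded status | Maintenance visits | 52-week status | Maintenance status |
|---|---|---|---|---|
| Reaches Week 52, stops | Yes | 0 | Complete | none |
| Leaves before Week 52 | No | 0 | Withdrawn | none |
| Reaches Week 52, continues | Yes | 1 or more | **none** | Complete |
| Reaches Week 52, continues | No | 1 or more | **none** | Withdrawn |
| TH, escapes, later maintenance visit | Yes | 1 or more | **none** | Complete |
| TH, escapes, later maintenance visit | No | 1 or more | **none** | Withdrawn |
| TH, escapes, no later visit | No | 0 | Withdrawn | none |

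The last row follows from the cut-point rule: the Escape visit itself counts in the 52-week phase, so it is not a maintenance visit.

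**Step 2. Compare with the study definition**

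Rows 3 and 4 are completers under Protocol Section 3.1 and SAP Section 13.7.1, but have no 52-week status under Section 13.6.2. Rows 5 and 6 are non-completers under the same definition, and also have none. If c subjects in a group reach Week 52 and k of them continue, the rule counts c − k as complete. For LTD, k = 0, so only TC and TH can be undercounted.

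**Step 3. Bound the size**

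Let m be the number of TH and TC subjects with at least one maintenance visit.
- Eligible for maintenance: 12 + 29 = 41.
- Subjects given a 52-week status: 80 − m.
- At m = 0, all 80 are classified. At m = 41, 80 − 41 = 39 are classified, which is the LTD group alone.
- Share without a 52-week status: 0/80 = 0% to 41/80 = 51%.

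The documents do not give m. It is probably below 41, because maintenance after Week 52 is open only where belimumab is not commercially available (Protocol Sections 3.1 and 5.6).

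**Step 4. Check after the fix**

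With completion taken from the study definition, and escape before Week 24 as its own row, each subject falls in exactly one of completed, escaped or withdrawn: 12 + 29 + 39 = 80.

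**The case against.** The best defence is that Section 13.6.2 describes the phase in which a subject left the study. Taken together, the four rules place every subject with a recorded status in exactly one cell, and Tables 1.5 and 1.6 are titled as displays of the conclusion record split by phase. On that reading nobody is lost: a subject absent from Table 1.5 appears in Table 1.6, and the fault is one of labelling. This is plausible, and it is true that affected subjects do get a maintenance-phase status. But no sentence in the SAP says phase of exit. Section 13.6.2 presents the rules as completion or withdrawal for the 52-week phase, and Section 6.1 relies on them for status by phase.

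It is also fair that the consequence is limited. The study is descriptive, and the time-to-flare analyses censor on flare assessment dates and death (SAP Section 7.1.4), not on this flag.

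Four stronger inferences are tempting, and the documents do not support them:
- A reader might infer that early escapes would be hidden. They would not: escape is its own analysis visit (Section 13.3.1) and a named phase cut-point (Section 13.4.1.1), escapers have no re-start phase (Section 13.4.1), and their compliance is set to missing (Section 13.6.2). What is lacking is an escape row in the 52-week disposition table.
- A reader might infer that every escaper falls outside the rule. One with no later maintenance visit is still classified.
- A reader might put a particular completion percentage on Table 1.5. Neither the number continuing nor the table's denominator is given, and the mock shells are not included.
- A reader might infer that the epoch table (Table 1.8) inherits the gap. No derivation for it is stated, so this cannot be settled either way. For the same reason Table 1.8 cannot be relied on as the remedy.

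**Conclusion.** The rule is wrong as written. Section 13.6.2 withholds a 52-week status from TH and TC subjects who reach Week 52 and continue, and from TH escapers with a later maintenance visit. That contradicts the definition of completion in Protocol Section 3.1 and SAP Section 13.7.1. Table 1.5, built on this rule, would omit these subjects and undercount completers in TH and TC but not in LTD.

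Between 0 and 41 of 80 subjects are affected, and the actual number is not in the documents. The conclusion assumes that Table 1.5 follows Section 13.6.2, as Section 6.1 indicates, and that the 80 enrolled are the ITT population. The primary time-to-flare result is not touched. The treatment-compliance derivation refers to subjects completing the 52-week phase and could pick up the same gap if it is programmed from this flag, but the SAP does not say that it is.

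**What to change.** In SAP Section 13.6.2, derive 52-week completion from the definition in Protocol Section 3.1 and SAP Section 13.7.1, whether or not the subject later has maintenance visits. For TH this means the holiday plus re-introduction to Week 52; for TC and LTD, all visits to Week 52. Use visit data for this, because the rules rest on a single completion status and that status may describe the end of maintenance for those who continue.

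Add a row to Table 1.5 for TH subjects who escaped before Week 24, counted as not completing the 52-week phase, whether or not they attended afterwards. All remaining subjects are withdrawn. State that the three categories sum to the group size, so that each of the 80 subjects has one 52-week status.

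Keep the maintenance-phase status as a separate derivation for Table 1.6.

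The cost is one derived flag and two lines of SAP text. It needs no new data and no change to study conduct.

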 - Any intrauterine device (IUD) or intrauterine system (IUS) with a documented failure rate of less than 1% per year;
 - Oral contraceptives (either combined or progesterone only);
 - Double barrier method with vaginal spermicidal agent: Condom and an occlusive cap (cervical cap/vault or diaphragm) with a vaginal spermicidal agent (foam/gel/film/cream/suppository);
 - Percutaneous contraceptive patch;
 - Male partner who is sterile prior to the female subject's entry into the study and is the sole sexual partner for the female subject.

Note: MMF and other forms of mycophenolate affect the metabolism of oral contraceptives and may reduce their effectiveness. As such, women receiving mycophenalate who are using oral contraceptives for birth control should employ an additional method (e.g., barrier method).

4. Informed consent: Able to provide written informed consent to participate.

CONFIDENTIAL

Additional eligibility criteria for subject enrolment in the treatment holiday and control groups in the study:

- SLE: achieve the required minimal disease activity criteria defined as SELENA SLEDAI score ≤3 after a minimum of 6 months of belimumab therapy (see Appendix 1 for SELENA SLEDAI).
- 2. **SLE Treatment:** Are on a stable SLE treatment regimen consisting of any of the following medications (alone or in combination) during the 30 day screening period prior to Day 0:
 - Corticosteroids (prednisone or prednisone equivalent)
 - Other immunosuppressive or immunomodulatory agents including methotrexate, azathioprine, leflunomide, mycophenolate (including mycophenolate mofetil, mycophenolate mofetil hydrochloride, and mycophenolate sodium), mizoribine, calcineurin inhibitors (e.g., tacrolimus, cyclosporine), sirolimus, oral cyclophosphamide, 6-mercaptopurine, or thalidomide.
 - Anti-malarials (e.g., hydroxychloroquine, chloroquine, quinacrine).
 - Non-steroidal anti-inflammatory drugs (NSAIDs), including sulfasalazine.
- 3. **Complement:** C3 and C4 complement levels at or above the lower limit of normal of the central laboratory reference range.

Additional eligibility criteria for subject enrolment in the **control group** in the study:

1. **Belimumab therapy:** Agree to continue receiving 10mg/kg belimumab intravenous infusions every 4 weeks. Subjects must be able to receive the first dose of belimumab in **this study** 4 weeks (minimum of 2 weeks, maximum of 8 weeks) after the last dose in their **previous** continuation study.

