5.5.2. Prohibited Medications and Non-Drug Therapies

Subjects in the **treatment holiday and control groups** who start prohibited medications or therapies at any time during the study must be withdrawn from the study. These subjects will return for the EXIT visit, and the follow-up visits 16 weeks and 6 months after receiving their last dose of belimumab as described in Section 4.4.

The following medications and therapies are prohibited at any time during the study:

- Other investigational agents (biologic or non-biologic). Investigational applies to any drug not approved for sale in the country in which it is being used.
- Co-enrolment into another study of an investigational agent or non-drug therapy that may interfere with the conduct of this protocol.
- Anti-TNF or anti-IL-6 therapy (e.g., adalimumab, etanercept, infliximab, tocilizumab).
- Other biologics (e.g., rituximab, abatacept, interleukin-1 receptor antagonist [anakinra]).

- Intravenous immunoglobulin (IVIG).
- IV cyclophosphamide.
- Plasmapheresis, leukapheresis.

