 unless there is evidence through comparison of partial dates to suggest otherwise, for example
 if the day is missing, then the month and year will be compared to the month and year of the
 first dose date of study treatment and if the month and year are the same or later, then the
 medication will be considered concomitant.

Allowable SLE Medications at Baseline

There are 5 medication categories that are evaluated. These medication categories are defined in the table below and stored in the variable CMSCAT. Only medications providing systemic exposure are evaluated. Systemic exposure is based on the route of administration. A flag variable for systemic exposure when CMSCAT is not blank is defined below and stored in the variable SYSTEMIC. The medication must have one of the defined medication categories below (CMSCAT ne blank) and must provide systemic exposure (SYSTEMIC='Y').

Medication Category (CMSCAT)	Rule
Anti-malarials	Set CMSCAT to "ANTIMALARIALS" if the preferred term begins with "QUINACRINE", "QUININE", "HYDROXYCHLOROQUINE", "MEPACRINE", or "CHLOROQUINE"
Steroids	Set CMSCAT to 'STEROIDS' if at least one associated ATC code (ATCCD1 – ATCCD6) begins with 'H02'

Allowable SLE Medications at Baseline	
Immunosuppressants	Set CMSCAT to 'IMMUNOSUPPRESSANTS' if at least one associated ATC code (ATCCD1 – ATCCD6) begins with 'L04A' or the preferred term begins with "CYCLOPHOSPHAMIDE" or "MERCAPTOPURINE".
NSAIDs	Set CMSCAT to NSAIDs if at least one associated ATC code (ATCCD1 – ATCCD6) begins with 'M01A'.
Aspirin	Set CMSCAT to "ASPIRIN" if CMDECOD contains "ACETYLSALICYLIC ACID" or "ACETYLSALICYLATE LYSINE".
Prohibited	Set to "PROHIBITED" if any of the following conditions are met, if CMDECOD equals "INVESTIGATIONAL DRUG", "IMMUNOGLOBULIN", "ADALIMUMAB", "ETANERCEPT", "INFLIXIMAB", "RITUXIMAB", "ABATACEPT", "ANAKINRA", "GOLIMUMAB", "CERTOLIZUMAB" and/or A review of the surgeries/procedures form indicates the subject had "PLASMAPHERESIS".
Traditional Chinese medications Glycosides of Paeony and Tripterygium	These medications will be identified based on a clinical review of all the concomitant medications assigned the following drug collection codes in the GSK drug dictionary: 50119401, 54654601, 40987301, 50192401, 53020201, 53060901, 53766001, 53927401, 53959101, 53959201, 53990601, 54619401, 54731901, 54908201, 59164101
Systemic (SYSTEMIC)	Rule
Blank	If CMSCAT=blank

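### The SAP rule that flags prohibited medication is narrower than Protocol 5.5.2; if that flag feeds time to first SFI flare, a protocol-defined event could be censored or dated too late

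*SAP*

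**What the plan says.** Protocol 5.5.2 prohibits investigational agents, co-enrolment in another investigational study, "Anti-TNF or anti-IL-6 therapy (e.g., adalimumab, etanercept, infliximab, tocilizumab"), "Other biologics (e.g., rituximab, abatacept, interleukin-1 receptor antagonist [anakinra"]), IVIG, "IV cyclophosphamide" and "Plasmapheresis, leukapheresis". Holiday and control subjects "who start prohibited medications or therapies at any time during the study must be withdrawn from the study".

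Protocol 8.1.2 treats a subject who receives a prohibited medication as having a flare on the date it is started. A subject who withdraws without a flare is censored at the last visit that measured flare. SAP 7.1.4 and the time-to-SFI-flare entry in SAP Appendix 7 (13.7.3) keep both rules. Neither says which medications are meant or refers to Protocol 5.5.2.

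SAP 13.6.2, in the table of allowable SLE medications at baseline, holds the only SAP rule that sets a category called PROHIBITED. It applies "if CMDECOD equals 'INVESTIGATIONAL DRUG', 'IMMUNOGLOBULIN', 'ADALIMUMAB', 'ETANERCEPT', 'INFLIXIMAB', 'RITUXIMAB', 'ABATACEPT', 'ANAKINRA', 'GOLIMUMAB', 'CERTOLIZUMAB", or when the surgeries/procedures form shows plasmapheresis. In the same table a medication becomes an immunosuppressant on an ATC code "or the preferred term begins with 'CYCLOPHOSPHAMIDE' or 'MERCAPTOPURINE", with no condition on route. The permitted list in Protocol 4.2 reads "sirolimus, oral cyclophosphamide, 6-mercaptopurine, or thalidomide", so it names only the oral form of cyclophosphamide. SAP 2.1 (Table 2) declares no change to what counts as prohibited.

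**The concern.** Whether a therapy is on the list decides whether a subject is an event or a censored observation in the primary endpoint. The protocol's list is partly by class and by route. The SAP's list is an exact match to ten dictionary terms plus one procedure. A programmer who looks in the SAP for the definition will find only 13.6.2, and following it would miss therapies that the protocol names. Starting one of them forces withdrawal in the holiday and control groups. A missed case with no flare would therefore leave the analysis as an ordinary censored withdrawal, and the flare percentage for that group would be too low.

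**Working it through.** No figure in the plan bears on this, so the check compares the two lists and then traces an omitted item through the endpoint rules.

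**Step 1. The lists side by side.**

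| Protocol 5.5.2 | SAP 13.6.2 PROHIBITED rule | Covered? |
|---|---|---|
| Investigational agents | INVESTIGATIONAL DRUG | Yes |
| Co-enrolment | none | No, but not a drug term |
| Anti-TNF | adalimumab, etanercept, infliximab, golimumab, certolizumab | Listed agents only |
| Anti-IL-6 (tocilizumab named) | none | **No** |
| Other biologics, as a class | rituximab, abatacept, anakinra | Protocol's examples only |
| IVIG | IMMUNOGLOBULIN | Yes |
| IV cyclophosphamide | none; coded IMMUNOSUPPRESSANTS | **No** |
| Plasmapheresis | procedures form | Yes |
| Leukapheresis | none | **No** |

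Golimumab and certolizumab are not named in the protocol but fit its anti-TNF class. The list was therefore extended beyond the protocol's examples in one class, while an agent the protocol names in another was left out. The systemic flag in 13.6.2 includes the intravenous route, so IV cyclophosphamide is handled exactly like the oral form.

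**Step 2. Path through the primary endpoint, if the 13.6.2 flag is used.** A holiday or control subject starts an omitted therapy and is withdrawn.
- No SFI flare recorded: Protocol 8.1.2 gives an event on the start date. SAP 7.1.4 would see no flare and no prohibited medication, and would censor at the last flare assessment.
- SFI flare recorded after the start: still an event, but on the flare date instead of the earlier start date.
- SFI flare recorded on or before the start: no difference.

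**Step 3. How often the first two branches could occur.** Protocol 6.3.1.3 makes new medication for disease activity one of the SFI variables, so many starts for lupus would already be flares (the exact criteria are redacted). Mainly starts for other reasons remain.

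**Step 4. Other endpoints.** For the flare rate (SAP 7.2.4.1) and the prednisone-day endpoints (7.2.4.3), withdrawal triggers the same imputation as a prohibited medication. The forced withdrawal therefore largely protects them in the holiday and control groups. SAP 7.3.4.3 also counts a prohibited medication as a renal-flare event, whereas the renal entry in Appendix 7 is silent on it.

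**Step 5. Weight of one subject.** SAP 2.3 gives 12 enrolled in the holiday group and 29 in control. SAP 7.1.5 displays the crude percentage with a flare.
- Holiday: 1/12 = 8.3 points.
- Control: 1/29 = 3.4 points.

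SAP Section 7 presents the holiday group by phase. All 12 start the holiday phase, so the weight there is also 8.3 points. The number entering re-start is not given; if 8 to 12 are assumed, one subject is 1/12 to 1/8, or 8.3 to 12.5 points.

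**The case against.** The strongest reply is that nothing shows 13.6.2 to be the endpoint rule. It sits in a baseline table, and 7.1.4 and 13.7.3 do not cite it. The prednisone rules in 7.2.4.3 speak of medication prohibited by the protocol, which points to Protocol 5.5.2. SAP 13.6.3 says that intra-articular steroids are identified for prohibited-medication rules. The systemic routes in 13.6.2 exclude that route, so 13.6.2 may not be the whole rule. Silence in Table 2 can be read as leaving the protocol definition in force. The display specification and the deviation plan are not in the documents and might hold the operative definition.

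A missed case could also surface elsewhere. Protocol 4.4 makes prohibited therapy a withdrawal reason to be recorded, Listing 5 reports withdrawal reasons, Listing 10 shows subjects on prohibited medication, and deviations are reviewed before the freeze (SAP 4.1).

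All of this stands and keeps the point conditional. It does not remove it. The one flag the SAP specifies gives the wrong value for therapies that the protocol names, and none of the detection routes is tied to the event derivation. If the flag is not used, an event component of the primary endpoint has no definition in the SAP. Either way the same cross-reference is needed.

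A reader might infer that the PROHIBITED row must exist for the endpoints, because the baseline usage summary in SAP 6.2 has no such category. That does not follow: NSAIDs and aspirin also have rows in 13.6.2 and are absent from that summary. Finally, Protocol 8.1.2 says medication, so whether leukapheresis counts is open. The SAP already includes plasmapheresis, however, and Protocol 5.5.2 lists the two together.

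**Conclusion.** The PROHIBITED rule in SAP 13.6.2 is wrong as written against Protocol 5.5.2. The severity is minor. The effect on the primary endpoint rests on two conditions: that this flag is used in 7.1.4, which the SAP does not say, and that a holiday or control subject starts an omitted therapy with no SFI flare already recorded. It would be too strong to say that the primary analysis uses the short list, or that every subject starting an omitted therapy is censored. The documents support neither. The number affected is unknown and may be zero. One such subject would move the displayed flare percentage by 8.3 points in the holiday group or 3.4 points in control. Results are descriptive, so no test is affected.

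**What to change.** State in SAP 7.1.4 and 7.3.4.3 that prohibited medication means any medication or therapy listed in Protocol 5.5.2. Align the 13.6.2 flag with that list: anti-IL-6 agents and other biologics by class, cyclophosphamide when the route is intravenous, and leukapheresis from the procedures form. Hold it as a separate flag so that the baseline medication categories do not change.

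Two items of clean-up belong with it. Reconcile the renal-flare entry in SAP Appendix 7 (13.7.3), which is silent on prohibited medication, with 7.3.4.3, which counts it as an event. Reconcile the intra-articular steroid remark in SAP 13.6.3 with Protocol 5.5.2, which does not list it.

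The cost is one sentence in each of two SAP sections and a few lines of code. The SAP already uses route of administration and the procedures form.
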